9.3.1. Hematology

Hematology will be conducted at screening, on Day 1 (before treatment administration), Day 15 (before treatment administration), and at Weeks 4, 8, 12 (EOS/ET) and Week 26 visits. Hematology will include red blood cell count, white blood cell count with differential count and percentages (including absolute neutrophil count), total hemoglobin, hematocrit, platelet count, and prothrombin time (sec) and prothrombin time (%).

Neutropenia is defined based on CTCAE severity grade 1 as, an absolute neutrophil count (ANC) of less than 1500 per microliter (1500/microL). A summary table will be provided based on the safety population.

9.3.2. Biochemistry

Biochemistry will be conducted at screening, on Day 1 (before treatment administration), Day 15 (before treatment administration), and at Weeks 4, 8, and 12 (EOS/ET) and Week 26 visits. Biochemistry will include creatinine, blood urea nitrogen, fasting serum glucose, serum FSH (for postmenopausal women), aspartate aminotransferase, alanine aminotransferase, gamma-glutamyl transpeptidase, total bilirubin, albumin, chloride, calcium, phosphorous, uric acid, total protein, sodium, and potassium.

9.3.3. Urinalysis

Urinalysis will be conducted at screening, on Day 1 (before treatment administration), Day 15 (before treatment administration), and at Weeks 4, 8, and 12 (EOS/ET) and Week 26 visits. Urinalysis will include specific gravity, pH, protein, glucose, and blood.

9.4. Vital Sign Measurements

Vital sign will be conducted at screening, on Day 1, Day 15, and at Weeks 4, 8, 12 (EOS/ET) and Week 26 visits. At Day 1 and Day 15 the Vital signs will be assessed every 30 minutes (\pm 5 minutes) during and end of infusion at time points Pre-dose, 30 min, 1 hr, 1.5 hrs, 2 hrs, 2.5 hrs, 3 hrs, 3.5 hrs, 4 hrs, 4.5 hrs, 5 hrs, 5.5 hrs, 6 hrs, 6.5 hrs, 7 hrs, 7.5 hrs and 8 hrs.

A summary table with actual values and change from baseline will be presented for vital sign data (systolic blood pressure (mmHg), diastolic blood pressure (mmHg), heart rate (beats/min), respiratory rate (breaths/min) and oral temperature ($^{\circ}$ C)) by scheduled visit and time point.

The indicative reference ranges for Systolic blood pressure: 90 – 140 mm Hg; Diastolic blood pressure: 50 – 90 mm Hg; Heart rate: 60 – 100 beats/min; Respiratory rate: 12 – 20 breaths/min; Temperature: 36 – 37.2 $^{\circ}$ C. Based on the ranges the parameters will be interpreted as below.

- Abnormal, Decreased, Clinically Significant
- Abnormal, Decreased, Not Clinically Significant
- Normal

- Abnormal, Increased, Clinically Significant
- Abnormal, Increased, Not Clinically Significant

A shift table comparing the interpretation at scheduled post-baseline visit and time point with those at baseline will be presented by visit and time point for the safety population.

All vital sign data will be listed by visit for safety population.

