 - a. Respiratory compromise (e.g., dyspnea, wheeze-bronchospasm, stridor, reduced peak expiratory flow or hypoxemia).
 - b. Reduced BP or associated symptoms of end organ dysfunction (e.g., hypotonia [collapse], syncope, incontinence).
2. Two or more of the following that occur rapidly after exposure to a likely allergen for that subject (minutes to several hours):
 - a. Involvement of the skin mucosal tissue (e.g., generalized hives, itch-flush, swollen lips-tongue-uvula).
 - b. Respiratory compromise (e.g., dyspnea, wheeze-bronchospasm, stridor, reduced peak expiratory flow, hypoxemia).
 - c. Reduced BP or associated symptoms (e.g., hypotonia [collapse], syncope, incontinence).
 - d. Persistent gastrointestinal symptoms (e.g., crampy abdominal pain, vomiting).
3. Reduced BP after exposure to known allergen for that subject (minutes to several hours):
 - a. Infants and children: low systolic BP (age specific) or greater than 30% decrease in systolic BP (this study is going to be conducted in adult subject population, hence this criterion will not be applicable here).
 - b. Adults: systolic BP of less than 90 mmHg or greater than 30% decrease from that person's baseline.

Note: Above differentiating features of IRRs, hypersensitivity and anaphylaxis are recommendations based on the literature ([Doessegger L and Banholzer ML 2015](#), [Khan DA](#)

2016, Sampson HA 2006). The investigator should use his/her clinical judgment to document it as IRRs and/or hypersensitivity reactions and/or anaphylaxis.

The timing and frequency of safety assessments are described in [Section 6.1](#).

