6.3.6 Vital Sign Measurements

Vital signs, including heart rate, seated BP, respiration rate, and oral body temperature, will be measured as detailed in [Table 14-1](#) and in the event of an IRR.

Blood pressure will be measured in the subject's arm and recorded to the nearest mmHg after the subject has been seated quietly for at least 2 minutes. The same arm and position should be used throughout the study, using an appropriate cuff size. All BP readings should be measured after resting for at least 5 minutes. When the timing of these measurements coincides with blood collection, the BP and heart rate should be obtained first.

Vital signs are to be obtained prior to each study treatment infusion, every 30 minutes (\pm 5 minutes) during infusion, at the end of infusion, and as clinically indicated. In the event of hypersensitivity reaction, vital signs should be obtained at additional time points until recovery per investigator judgment.

6.3.7 12-Lead Electrocardiogram

Twelve-lead ECGs will be performed as indicated in [Table 14-1](#) under medical supervision. Before recording, subjects should be resting in a quiet supervised setting with minimal

stimulation (e.g., no television, loud music, and computer games) and lie in a resting position for 10 minutes before ECG recording.

All ECGs are to be read locally with local ECG equipment by an appropriately qualified and experienced ECG reader at the study site.

Corrected QT interval (QTc) value will be calculated using the Fridericia formula ($QTc = QT/(RR^{-1/3})$), QTc should be expressed in milliseconds, the provided formula assumes QT also in milliseconds and RR in seconds. The QTc interval will be automatically calculated. In the case of clinically significant ECG abnormalities, the investigator should report these as an AE if not due to a preexisting condition or if a preexisting condition worsens in frequency or intensity.

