3.1. Overall Study Design and Plan

This study is a phase 3, randomized, double-blind, parallel group, multicentre study to assess the immunogenicity and safety of two 1000 mg IV infusions of DRL₁RI or continued treatment with Rituxan[®] or MabThera[®] in approximately 140 subjects (70 per treatment arm) in transitioning to biosimilar Rituximab (DRL₁RI) or continued treatment with Rituxan[®] or MabThera[®].

Baseline is defined as the last available value prior to the first dose of study drug administration. For Vital Sign timepoint assessment are scheduled on Day 1 and Day 15, if the time is missing then Day 1 Pre-dose will be considered as baseline.

The study will include screening period (Days -14 to 0) and a double-blind period (Day 1 to Week 12), which consist 2 weeks of treatment period and 10 weeks of follow-up period for safety and immunogenicity. An additional follow-up visit will be conducted at Week 26 to evaluate safety and to perform a serum pregnancy test in women of childbearing potential (WOCBP).

Re-screening will be allowed for those subjects who do not meet the criteria for participation in this study (screen failure) at the investigator's discretion, following discussion with the sponsor designee medical monitor.

Eligible subjects will be randomized in permuted blocks in 1:1 ratio by interactive web response system (IWRS) to receive either two 1000 mg infusions of DRL_RI (Arm A) or US-rituximab/EU-rituximab (Arm B) on Day 1 and Day 15. Randomization schedule will be stratified by region (US/EU).

[figure not shown]
Subjects having signed the informed consent form (ICF) versions prior to the protocol version 3.0, Amendment 2 need to re-consent to continue participating in the study after Week 12 through Week 26. If a subject does not re-consent for further study participation after Week 12, then his/her study data up to Week 12 will be collected and the subject will be discontinued from the study.

Study procedures include physical examination, vital signs measurement, clinical laboratory assessments, AEs, and concomitant medication. All subjects completing the study at Week 12 or those discontinuing the study before Week 12 will attend an EOS/early termination (ET) visit. Furthermore, subjects completing the follow-up at Week 26 or discontinued after Week 12 will attend Week 26/early termination (ET) visit.

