Continuous data will be described using descriptive statistics (i.e. n, mean, standard deviation [SD], median, quartiles, minimum, and maximum). Categorical data will be described using the count and percentage in each category. For the summary statistics of all numerical variables unless otherwise specified, minimum and maximum will be displayed to the same level of precision as reported. Mean and median will be displayed to one level of precision greater than the data collected. Standard deviation will be displayed to two levels of precision greater than the data collected.

When count data are presented, the percentage will be suppressed when the count is zero in order to draw attention to the non-zero counts. A row denoted “Missing” will be included in count tabulations where specified on the shells to account for missing values. The denominator for all percentages will be the number of subjects within the analysis population of interest, unless otherwise specified. Percentages will be presented to one decimal place.

For Time Matched Rituximab Concentrations (TMRC) sample, concentration below the lower limit of quantification (BLLOQ) will be converted to '0' for the purpose of quantitative summaries, but will be presented as recorded, i.e. BLLOQ in listings.

Data will be displayed in all listings sorted by subject number and visit, if applicable. Listings will include all visits including unscheduled visits.

"No data available for this report" will be presented when there are no data available to report.

Unless otherwise specified, baseline will be defined as the last non-missing value collected before the first study drug administration. Study day is defined as:

- Visit/examination date – date of first study drug administration when date is prior to the date of first study drug administration (day 1).
- Visit/examination date – date of first study drug administration + 1 when date is on or after day 1.

For summaries by visit, if multiple records fall on the same visit and timepoint, then the record which is the earliest value will be chosen.

Unscheduled results will not be summarized but will be listed, unless otherwise specified. Post baseline summaries will include all values collected after the date of first study drug administration.

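### Day 15 infusion vital signs are reported as change from the pre-first-dose value, most late time points hold mainly slowed or interrupted infusions, and there is no end-of-infusion row or per-subject worst-value table.

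*SAP*

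**What the plan says.** **Baseline.** SAP 3.1: "Baseline is defined as the last available value prior to the first dose of study drug administration". For vital signs it adds a fallback: "if the time is missing then Day 1 Pre-dose will be considered as baseline". SAP Section 4 (General Statistical Considerations) gives the same rule for all data unless otherwise specified: "baseline will be defined as the last non-missing value collected before the first study drug administration". SAP 9.4 specifies nothing different for Day 15.

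**Time grid and summaries.** SAP 9.4 has readings on Day 1 and Day 15 "during and end of infusion at time points Pre-dose, 30 min, 1 hr, 1.5 hrs, 2 hrs", continuing half-hourly to "6 hrs, 6.5 hrs, 7 hrs, 7.5 hrs and 8 hrs". The same grid serves both infusions. "A summary table with actual values and change from baseline will be presented for vital sign data", and a shift table follows, both by visit and time point.

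**Readings required.** Protocol 6.3.6 asks for vital signs before each infusion, every 30 minutes (±5 minutes) during it, "at the end of infusion, and as clinically indicated". It also asks for additional readings during a hypersensitivity reaction. Protocol 5.2.3 requires at least one hour of observation after the dose but attaches no vital-sign schedule to that hour.

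**Summary rules (SAP Section 4).** Unscheduled results are listed and not summarised. If several records share a visit and time point, the earliest is used. Percentages use the analysis population as denominator. All three apply unless otherwise specified.

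**Endpoint status.** Protocol Table 2-1 and SAP 3.2 place vital signs among the other safety endpoints. Infusion-related, hypersensitivity and anaphylactic reactions are primary safety endpoints.

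**The concern.** Readings every 30 minutes during an infusion are there to show what that infusion does to blood pressure, heart rate, respiration and temperature. Three features of the plan blur this.

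- **Day 15 reference.** Change and shift on Day 15 combine the effect of the second infusion with whatever moved between the two visits, including any effect of the first 1000 mg. The same-day pre-dose reading separates the two but is not used as the reference.
- **Late rows.** One 8-hour grid is applied to infusions that should end much earlier. Subjects still being measured at late points are mainly those whose infusion was slowed or interrupted. Slowing and interruption follow infusion reactions, so this group is selected after randomisation by something close to the outcome of interest.
- **Readings without a place in the tables.** The end-of-infusion reading matches no listed time point. Extra readings taken during a reaction are unscheduled and reach only the listings. Laboratory data get a worst post-baseline summary in SAP 9.3; vital signs get no per-subject equivalent.

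What is at stake is how well the measured data can support or question the reported infusion reactions, arm by arm and infusion by infusion.

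**Working it through.** The documents state no infusion duration, so there is no plan figure to reproduce. The duration follows from the stated rates.

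**Inputs.** Dose 1000 mg per infusion. Day 1: start at 50 mg/h, add 50 mg/h every 30 min, maximum 400 mg/h. Day 15: start at 100 mg/h, add 100 mg/h every 30 min, same maximum (Protocol 5.2.3 and SAP 7.2 agree). Grid after the start: 0.5 to 8 h in half-hour steps, 16 points per infusion, 32 in all (SAP 9.4).

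**Formula.** Amount given in each half hour = rate × 0.5 h, summed until 1000 mg is reached.

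- Day 1: 25 + 50 + 75 + 100 + 125 + 150 + 175 = 700 mg by 3.5 h. The remaining 300 mg at 400 mg/h takes 0.75 h. End at **4.25 h**.
- Day 15: 50 + 100 + 150 = 300 mg by 1.5 h. The remaining 700 mg at 400 mg/h takes 1.75 h. End at **3.25 h**.

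**Grid points after the end of an unslowed infusion**

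| | During | After | After, allowing the 1 h observation |
|---|---|---|---|
| Day 1 | 8 (0.5–4.0 h) | 8 (4.5–8 h) | 6 (5.5–8 h) |
| Day 15 | 6 (0.5–3.0 h) | 10 (3.5–8 h) | 8 (4.5–8 h) |
| Total | 14 of 32 | **18 of 32 (56%)** | **14 of 32 (44%)** |

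The ±5-minute window changes nothing: the 4.5 h reading taken five minutes early is at 4 h 25 min, still after 4 h 15 min, and likewise for 3.5 h on Day 15.

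**How far from plan the last rows are.** Still being on infusion at 8 h needs a mean rate of 1000/8 = 125 mg/h or less. That is a delay of 8 − 4.25 = 3.75 h on Day 1 or 8 − 3.25 = 4.75 h on Day 15.

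**Sensitivity to local labelling.** The documents give no alternative rates, so these are assumptions. If Day 15 ran at the Day 1 rates it would end at 4.25 h, and 8 + 8 = 16 of 32 points would be late. If every rate were halved, the infusions would end at 6.75 h and 5.75 h, leaving 3 + 5 = 8 of 32.

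**Likely size of the late groups (assumption).** With 70 per arm and 5% to 23% slowed, 3.5 to 16.1, so about 4 to 16 subjects per arm. The 23% is the rate of infusion reactions at the first infusion of first exposure in Protocol 1.1.1.4. Everyone here has had rituximab before, so it serves as an illustrative ceiling. Under the default denominator, 2 shifts among 4 measured subjects would print as 2/70 = 2.9%, not 2/4 = 50%.

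**End of infusion.** 4 h 15 min and 3 h 15 min each lie 15 minutes from the nearest grid point, outside the ±5-minute window, and the SAP has no rule assigning them to a row.

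**Age of the Day 15 reference.** Day 15 minus Day 1 is 14 days, or 15 with the +1 day window. A same-day reference makes it zero. On Day 1 the pre-dose reading is normally the baseline already, so Day 1 changes are not affected.

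**The case against.** A fair defence of the plan has several good points.

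- **Extremes are visible.** A reader might infer that a brief pressure fall in one subject is averaged away. It is not: SAP Section 4 includes minimum and maximum in the descriptive statistics, so the lowest value and the largest fall appear at each time point. What is missing is a per-subject count over the whole infusion.
- **The hypotension criterion is partly covered.** A reader might infer that "systolic BP of less than 90 mmHg or greater than 30% decrease from that person's baseline" (Protocol 6.3) is never tabulated. Systolic pressure below 90 mmHg enters the SAP 9.4 shift categories, and SAP 9.1.9 with Table 14.3.1.2.9.5 covers the anaphylaxis criteria for events classified as anaphylactic. Only the fall of more than 30% outside such events has no count.
- **Reactions are captured elsewhere.** Infusion reactions come from eCRF-classified events (SAP 9.1.8). Protocol 6.3.2 makes a vital-sign abnormality an adverse event if it brings symptoms, further testing or intervention, or interruption of treatment. Vital signs are not the only evidence, and all readings are listed.
- **No bias between arms from the old baseline.** Both randomised arms use the same rule. Actual values at Day 15 pre-dose and later let a reader follow the mean course. Within-subject change, its spread and same-day shifts are still lost.
- **Late rows are not exclusively slowed infusions.** End-of-infusion readings may be entered at the next grid point, other readings may be taken as clinically indicated, interruptions can have other causes, and local labelling may alter the rates. n is shown with continuous summaries. This supports 'mainly', not 'only'.

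A gain in precision is also tempting to claim, but the documents give no correlations. With assumed correlations of 0.5–0.7 between days and 0.7–0.85 within a day, the variance ratio (1 − r within)/(1 − r between) runs from 0.15/0.5 = 0.3 to 0.3/0.3 = 1.0, so it could be no gain at all.

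**Conclusion.** The point holds as a weakness of a descriptive analysis. As written, within-subject change and shift for the second infusion are not reported, although the reading needed for them is collected. On the stated rates 18 of 32 infusion time points, or 14 of 32 with the observation hour allowed, describe mainly prolonged infusions, and differences between arms there should not be read as randomised comparisons. The end-of-infusion reading has no row, and no per-subject worst value or count of falls above 30% is planned across all treated subjects.

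The counts rest on the rates in Protocol 5.2.3 and would shrink if local labelling gave slower ones. The documents do not support a claim that the arm comparison is biased by the old baseline, that severe falls go unseen, or that the primary analysis of infusion reactions is affected.

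**What to change.** Amend SAP 9.4 as follows.

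1. For Day 15 infusion time points, add change and shift from the Day 15 pre-dose value. Keep the pre-first-dose baseline for later visits.
2. Add an end-of-infusion row for each infusion. Keep the late rows, show n in each, and base percentages on subjects measured. Footnote that rows after 4 h (Day 1) and 3 h (Day 15) mainly reflect prolonged infusions and are not randomised comparisons. Moving these rows to listings would be worse, because it would drop tabulated safety data from slowed infusions.
3. Add one table by arm and infusion of each subject's worst on-infusion value (lowest systolic and diastolic pressure; highest heart rate, respiratory rate and temperature), including unscheduled readings. Give the number with systolic pressure below 90 mmHg or a fall of more than 30% from same-day pre-dose. The denominator is subjects who started that infusion.

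In the same edit, reconcile the sentence in SAP Section 4 that limits post-baseline summaries to values after the date of first administration. Read literally, it excludes the Day 1 infusion readings that 9.4 tabulates.

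The cost is SAP wording, one extra table and some programming. No new data are needed.

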3.1 Study Design

3.1.1 Description

This is a randomized, double-blind, parallel group, multicenter, Phase 3 transition study in subjects with active RA who are eligible for the subsequent treatment course with US-rituximab or EU-rituximab according to the clinical judgment of the investigator.

It is planned to randomize 140 subjects (70 per treatment arm) at approximately 50 sites in up to 7 countries (including, but not restricted to the United States).

A course of treatment with US-rituximab or EU-rituximab in RA consists of two 1000 mg IV infusions separated by 2 weeks. Subjects with RA who have received at least 1 full course comprising two 1000 mg infusions with either US-rituximab or EU-rituximab will be eligible for the study. The rituximab reference product (US-licensed rituximab [Rituxan] or EU-approved rituximab [Mabthera]) used should be the same in the prior and the randomized treatment course, respectively. Subjects having received the prior treatment course with reference products other than US-licensed rituximab (Rituxan) or EU-approved rituximab (Mabthera) will not be eligible for the study. Subjects should not be switched from the prior to the randomized treatment course from US-licensed to EU-approved reference product or vice versa.

Subjects will then be randomized by interactive web response system (IWRS) to receive either two 1000 mg infusions of DRL_RI (Arm A) or US-rituximab/EU-rituximab (Arm B) on Day 1 and Day 15. This will constitute the next course of rituximab treatment. Subjects randomized to Arm A will receive DRL_RI and subjects randomized to Arm B will continue to receive either US-rituximab or EU-rituximab.

The study will consist of a screening period (Days -14 to 0) and a double-blind period (Day 1 to Week 12). Subjects will attend a screening visit followed by visits at Weeks 0 (Day 1), 2, 4, 8, and 12 (end of study [EOS]) after randomization. An additional follow-up visit will be conducted at Week 26 to evaluate safety and to perform a serum pregnancy test in women of childbearing potential (WOCBP).

[figure not shown]
Subjects having signed the informed consent form (ICF) versions prior to the one introduced by this amendment need to re-consent to continue participating in the study after Week 12 through Week 26. If a subject does not re-consent for further study participation after Week 12, then his/her study data up to Week 12 will be collected and the subject will be discontinued from the study.

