5.2.3 Study Treatment Administration

Study treatments (DRL_RI or US-rituximab/EU-rituximab) will be administered by IV infusion using the escalating infusion rate described in the Health Authority-approved product

labels for US-rituximab/EU-rituximab. The infusion rate must be well controlled to reduce the incidence of serious IRRs.

Only qualified personnel who are familiar with procedures that minimize undue exposure to them and to the environment should undertake the preparation, handling, and safe disposal of biological agents.

Study treatment infusions should be administered under close medical supervision and in an environment where full resuscitation facilities are immediately available. Vital signs will be monitored every 30 minutes (\pm 5 minutes) during the course of the treatment administration or more frequently as necessary.

The study treatments will be administered as two 1000 mg IV infusions on Day 1 and Day 15.

Below instructions should be followed in consolidation with the local product labelling if it differs from these instructions.

- **First infusion (Day 1):** Initiate infusion at a rate of 50 mg/hour. In the absence of infusion toxicity, increase infusion rate by 50 mg/hour increments at 30-minute intervals, to a maximum of 400 mg/hour.
- **Second infusion (Day 15):** Initiate infusion at a rate of 100 mg/hour. In the absence of infusion toxicity, increase rate by 100 mg/hour increments at 30-minute intervals, to a maximum of 400 mg/hour.
- Subjects should be closely monitored post-dose for at least 1 hour for the onset of IRRs. Subjects who develop evidence of severe reactions, especially severe dyspnea, bronchospasm, or hypoxia should have the infusion interrupted immediately. In all subjects, the infusion should not be restarted until complete resolution of all symptoms and normalization of laboratory values is achieved. At this time, the infusion can be initially resumed at not more than one-half the previous rate. If the same severe reactions occur for a second time, the decision to stop the treatment should be seriously considered on a case-by-case basis.
- Mild to moderate IRRs usually respond to a reduction in the rate of infusion. The infusion rate may be increased upon improvement of symptoms.

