6.3.2 Abnormal Laboratory Values/Vital Signs Measurements/Electrocardiograms

Laboratory/vital signs/ECG abnormalities should be reported as an AE/SAE if any 1 of the following criteria is met:

- Result is associated with signs/symptoms;
- Requires additional diagnostic testing and/or interventions;
- Leads to a change in dose, discontinuation of, or interruption to the study treatment.

Repeats of an abnormal test result without any of the above criteria do not constitute an AE.

Any test result determined to be an error is not required to be reported as an AE.

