9.3. Clinical Laboratory Evaluations

Clinical laboratory (biochemistry, hematology and urinalysis) test samples will be analyzed at the local laboratory. All summaries and listings will be presented in SI units.

If any laboratory value falls above or below the upper or lower level of quantification, the value of the upper or lower level of quantification will be taken (e.g. <0.5 will become 0.5) for summaries but left as recorded in the listing.

Actual value and change from baseline of all numeric laboratory parameters including clinical chemistry, hematology, urinalysis will be summarized using descriptive statistics in separate tables, by test parameter and visit.

The assessment at Day 1 and Day 15 for all the laboratory parameters will be conducted before the treatment administration.

All relevant clinical laboratory tests will be interpreted as below.

- Abnormal, Decreased, Clinically Significant
- Abnormal, Decreased, Not Clinically Significant
- Normal
- Abnormal, Increased, Clinically Significant
- Abnormal, Increased, Not Clinically Significant

These categorical data will be summarized in shift tables comparing the results at each scheduled post-baseline visit with those at the baseline visit. A row denoted “Missing” will be included in count tabulations where specified on the shells to account for dropouts and missing values.

The denominator for all percentages will be the number of subjects in that treatment within the safety population. Unless otherwise specified, baseline will be defined as the last non-missing evaluation prior to or on the date that the first dose of treatment is taken.

The numeric parameters will be graded using CTCAE v5.0, where applicable. The CTCAE grades for analysis will be Grade 1 (Mild), Grade 2 (Moderate), Grade 3 (Severe) and Grade 4 (Life-threatening). The CTCAE Grade 5 (Death) will not be applied in this analysis since death cannot be determined from a numeric laboratory result. Unit conversion will be performed if the clinical laboratory unit is not consistent with the unit in CTCAE v5.0. These grades will be summarized in shift tables comparing worst post baseline visit grade with those at the baseline visit.

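### Infusion-day vital signs are summarised only time point by time point, so the planned tables do not give the number of subjects per arm with any out-of-range reading during an infusion

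*SAP*

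**What the plan says.** Protocol 6.3.6 asks for vital signs before each infusion, every 30 minutes (±5 minutes) during it, "at the end of infusion, and as clinically indicated". It also asks for extra readings during a hypersensitivity reaction.

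SAP 9.4 describes the Day 1 and Day 15 readings as taken "during and end of infusion at time points Pre-dose, 30 min, 1 hr, 1.5 hrs, 2 hrs, 2.5 hrs", and the list continues in half-hour steps to 8 hours. That makes 16 times after pre-dose, none of them named as the end of infusion. Two summaries follow. One gives actual values and changes by visit and time point. Of the other the SAP says: "A shift table comparing the interpretation at scheduled post-baseline visit and time point with those at baseline will be presented by visit" and, as the sentence goes on, by time point. In SAP 12.2 these are Tables 14.3.4.3.1 and 14.3.4.3.2, and no other vital-sign table is listed. All readings go into Listing 16.2.9.1. SAP section 4 lists unscheduled results but does not summarise them.

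For laboratory data, SAP 9.3 does plan a once-per-subject summary, "comparing worst post baseline visit grade with those at the baseline visit".

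**The concern.** Vital signs are a listed safety endpoint (Protocol Table 2-1, SAP 3.2), and hypotension, hypertension and tachycardia are among the IRR signs named in Protocol 6.3. Changes during an infusion can be brief and can start at different times in different subjects. A table for each half-hour spreads them over many cells. The cells cannot be added to give a number of subjects, because one subject may be out of range at several times. The natural question for a transition study is how many subjects in each arm had a low systolic pressure or a fast heart rate during the first infusion of the new product. The two vital-sign tables do not answer it.

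The end-of-infusion reading raises a smaller question: the protocol requires it, but the SAP does not say where it is tabulated.

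**Working it through.** The plan states no rate for out-of-range vital signs, and its sample-size text is redacted, so there is no figure to reproduce. Two direct checks apply.

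**Inputs**
- Subjects per arm: 70. Protocol 3.1.1: "It is planned to randomize 140 subjects (70 per treatment arm".
- Dose: 1000 mg per infusion. Protocol 5.2.3: "The study treatments will be administered as two 1000 mg IV infusions on Day 1 and Day 15".
- Rates (Protocol 5.2.3, SAP 7.2): Day 1 starts at 50 mg/h and rises by 50 every 30 minutes; Day 15 starts at 100 mg/h and rises by 100 every 30 minutes; the maximum is 400 mg/h on both days.
- Listed times: every half-hour from 0.5 h to 8 h (SAP 9.4).

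**1. When does an unslowed infusion end?**
- Day 1: (50 + 100 + 150 + 200 + 250 + 300 + 350) × 0.5 = 700 mg by 3.5 h. The remaining 300 mg at 400 mg/h takes 0.75 h. End: 4.25 h.
- Day 15: (100 + 200 + 300) × 0.5 = 300 mg by 1.5 h. The remaining 700 mg at 400 mg/h takes 1.75 h. End: 3.25 h.

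The nearest listed times are 4.0 and 4.5 h on Day 1, and 3.0 and 3.5 h on Day 15, each 15 minutes away. During the infusion there are 8 listed times on Day 1 (0.5 to 4.0 h) and 6 on Day 15 (0.5 to 3.0 h).

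SAP section 4 keeps the earliest record when several fall on one visit and time point. If the end reading were assigned back to the preceding half-hour, the routine reading would be kept and the end reading would drop out of the summary.

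**2. What do the per-time-point counts say about subjects?**

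Let c(j) be the number abnormal at time j among n subjects. The number of subjects abnormal at least once is at least the largest c(j), if the same subjects recur. It is at most the sum of the c(j), capped at n, if they are all different.

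As an illustration, assume c(j) = 1 at every time during the infusion, with n = 70:

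| Infusion | Times | Each cell | Lowest subject incidence | Highest subject incidence |
|---|---|---|---|---|
| Day 1 | 8 | 1/70 = 1.4% | 1/70 = 1.4% | 8/70 = 11.4% |
| Day 15 | 6 | 1/70 = 1.4% | 1/70 = 1.4% | 6/70 = 8.6% |

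Two arms could show the same Day 1 cell counts and still differ by up to 8 − 1 = 7 subjects (7/70 = 10.0 percentage points).

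**The case against.** A reader might infer that the incidence of hypotension or tachycardia in each arm is never shown, or that a real difference between arms would appear in no table. The documents do not support either.

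- **Reported events are counted per subject.** Protocol 6.3.2 calls for an AE report when an abnormality has symptoms, needs testing or intervention, or changes treatment. SAP 9.1.1 and 9.1.7 to 9.1.9 count subjects with TEAEs, hypersensitivity reactions, IRRs and anaphylaxis. The protocol's anaphylaxis threshold, "systolic BP of less than 90 mmHg or greater than 30% decrease from that person's baseline", is one of the criteria behind Table 14.3.1.2.9.5. This stands.
- **Asymptomatic falls are not clearly shut out of AE reporting.** The sentence "Repeats of an abnormal test result without any of the above criteria do not constitute an AE" concerns repeat tests. The AE definition in Protocol 6.3.1.1.1 covers any unfavourable sign, and Grade 1 in 6.3.1.3 includes asymptomatic findings. The vital-sign tables therefore cannot be called the only summary of such falls. This stands.
- **The readings do appear.** They are in the shift cells and the listing. If each affected subject had a single abnormal reading, adding the cells would recover the subject count exactly. The ambiguity arises when readings recur in a subject, and the documents give no rate of recurrence. This stands.
- **The plan does what the protocol asks.** Protocol 7.4.6 asks for change from baseline by arm and visit, and vital signs are an other, not a primary, safety endpoint. The laboratory summary in SAP 9.3 uses CTCAE grades, so the lack of a vital-sign equivalent is not a contradiction. This stands.
- **The end-of-infusion row may exist.** The SAP refers to table shells that are not among the documents. The ±5 minutes is a tolerance for taking readings; no SAP rule uses it to assign them to rows. Local labelling may also change the infusion time. The gap is in the SAP text and is not shown to be in the output.

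Some of the gap remains. Classification as an IRR, hypersensitivity or anaphylaxis rests on investigator judgment (Protocol 6.3), and measured values are an objective check on it. An event coded under one IRR term may not show its component signs: SAP 9.1.8 promises a summary of signs and symptoms, but SAP 12.2 lists no separate table for it. Extra readings taken during a reaction may count as unscheduled, and then they would only be listed.

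**Conclusion.** The point holds as a cheap improvement of minor severity. The per-subject, per-infusion incidence of measured out-of-range vital signs cannot be read from Tables 14.3.4.3.1 and 14.3.4.3.2. Only abnormalities reported as AEs, IRRs, hypersensitivity or anaphylaxis are counted once per subject. In the illustration the tables leave a range of 1.4% to 11.4% on Day 1 and 1.4% to 8.6% on Day 15. Separately, the SAP list does not name the end-of-infusion reading that the protocol requires.

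The figures assume 70 subjects per arm, infusions run without slowing at the stated rates, and one abnormal reading at each listed time. The last is an illustration, not a forecast: the documents give no expected rate. The width of the range depends on it, but the inability to count subjects from separate time-point tables does not.

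The documents do not show that a safety signal would be lost or that a required analysis is missing.

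**What to change.** In SAP 9.4 and 12.2:

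1. Add one table per infusion (Day 1 and Day 15), by arm, with the subjects who started that infusion as denominator. Give the number and percentage with at least one value outside the SAP 9.4 ranges after the start of infusion, by parameter and by direction (low or high). Include end-of-infusion and unscheduled infusion-day readings, and say so explicitly, because SAP section 4 otherwise leaves unscheduled results out of summaries.
2. In the same table, summarise the lowest systolic pressure and the highest heart rate per subject.
3. Name the end of infusion as its own time point in Tables 14.3.4.3.1 and 14.3.4.3.2. If the shells already have that row, only the SAP text needs to change.

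The cost is SAP wording and one or two extra tables from data already collected; study conduct does not change. There is one small downside. Subjects with longer or interrupted infusions have more readings, and so a slightly higher chance of any abnormal value. A footnote should state this.
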